#### Part 2

....

Frel will be calculated using Cmax(first dose), Cmax(second dose), AUC(0-24), AUC(0-12), AUC(12-24), AUC(0-last) and AUC(0-inf). If for any reason the AUC(0-inf) is not calculable then an alternative AUC over a partial area may be used.

The following Frel comparison will be made:

• KD025 200 mg BID + omeprazole (Period 2) vs KD025 200 mg BID alone (Period 1)

Metabolite to parent ratios (MPR) after a single dose administration will be calculated as follows using Cmax and AUC(0-inf) for Part 1 and Cmax(first dose), Cmax(second dose) and AUC(0-inf) for Part 2. If for any reason the AUC(0-inf) is not calculable then an alternative AUC such as AUC(0-last) or AUC over a partial area may be used:

 $MPR = \frac{AUC \text{ or } Cmax \text{ (metabolite)}}{AUC \text{ or } Cmax \text{ (parent)}} \times \frac{MW \text{ (parent)}}{MW \text{ (metabolite)}}$ 

Reporting and Analysis Plan KD025-107 (QSC200311) Final v2.0 09 Nov 2018 Page 25 of 99

SPS952 T1 v2 RAP Template

Correcting for molecular weight (MW):

- Parent MW = 452.52 g/mole
- KD025m1 MW = 410.44 g/mole
- KD025m2 MW = 411.42 g/mole

#### 9.2 Pharmacokinetic Parameter Reporting Specifications

The following flags/footnotes may be applied to the PK parameters:

Flag	Footnote	
а	Rsq of regression was <0.9	
b	Period used for regression analysis was less than 2-fold the calculated half-life	
с	Extrapolated portion of AUC(0-inf) >20%	
d	Insufficient post-Cmax data points for estimation of lambda-z	
е	Entire profile BLQ, no pharmacokinetic parameters could be calculated	

In the event that a reliable lambda-z cannot be determined or the extrapolated portion of AUC(0-inf) >20%, then the parameter estimates derived using lambda-z and/or AUC(0-inf) may be deemed unreliable and excluded from the summary statistics and formal statistical analysis.

Additional flags may be applied based on emerging data.

Separate summary tables, figures and listings will be produced for each study part.

#### 9.2.1 Bioanalytical and Pharmacokinetic Summary Tables

Summary statistics (ie mean, SD, coefficient of variation [CV%], median, minimum, maximum, n, geometric mean, geometric SD, geometric CV% and geometric n) will be calculated for plasma concentrations by time point for each treatment and analyte. This data will be summarised for the parent KD025 and its metabolites (KD025m1 and KD025m2) on different tables.

Imputation of non-numerical values reported in the plasma concentration data (ie values that are BLQ), will be entered as zero for the determination of summary statistics with the exception of geometric mean parameters where BLQ values will be imputed as half the LLOQ value (except for pre-dose samples on Day 1 which will not be summarised). Data recorded as NR or NS will be handled as missing, ie no assumption will be made about the actual concentration. If applicable, data recorded as not calculated (NC) will be handled as missing.

Concentration data recorded as NR (as by the bioanalytical laboratory) will be queried to ascertain any underlying cause and further imputation may be made if appropriate (eg concentrations above the upper limit of quantification may be set to the upper limit or diluted for reanalysis as appropriate).

Summary statistics (ie mean, SD, CV%, median, minimum, maximum and n) will be presented for all PK parameters for plasma for each treatment and analyte. Also geometric mean, geometric SD, geometric CV% and geometric n will be presented for all PK parameters (except Tlag and Tmax) for each treatment and analyte. This data will be summarised for the parent KD025 and its metabolites (KD025m1 and KD025m2) on different tables.

#### 9.2.2 Bioanalytical and Pharmacokinetic Figures

These data will be plotted separately for the parent KD025 and its metabolites KD025m1 and KD025m2 and will use the PK population throughout unless otherwise stated.

Arithmetic mean plasma concentration vs time curves will be produced on a linear/linear scale and error bars for  $\pm$  arithmetic SD will be included on the plots.

Geometric mean plasma concentration vs time curves will be produced on a  $log_{10}$ /linear scale. Error bars will be included on these plots, where error bars are (geometric mean ×/÷ geometric SD).

Both arithmetic mean and geometric mean plots will be produced for the following:

#### Part 1

- all four treatments on the same plot, with separate plots for KD025 and its metabolites (3 plots)
  - each plot will represent an analyte: KD025 (parent), KD025m1 (metabolite 1), KD025m2 (metabolite 2)
  - 4 lines on each plot with each line representing a treatment
- both treatments for the relevant treatment comparisons on the same plot, with separate plots for each comparison and for KD025 and its metabolites (9 plots)
  - 3 treatment comparisons (see Section 9.1.2), 3 plots for each treatment comparison
  - each plot representing a study comparison: itraconazole effect (Period 2 vs Period 1), rabeprazole effect (Period 3 vs Period 1) and rifampicin effect (Period 4 vs Period 1) using the appropriate PK analysis dataset
  - 2 lines on each plot with each line representing a treatment
- KD025 and its metabolites on the same plots, with separate plots for each treatment (4 plots)
  - each plot representing a treatment
  - 3 lines on each plot with each line representing an analyte: KD025 (parent), KD025m1 (metabolite 1), KD025m2 (metabolite 2)

#### 9.2.3 Bioanalytical and Pharmacokinetic Listings

The sample collection data (eg collection times) for PK samples will be listed. In addition, all concentration data and PK parameters will be listed on a per subject basis. Any flags used will be listed with the appropriate definition. BLQ values will be reported as BLQ in the data listings.

#### 9.2.4 Statistical Analysis of Pharmacokinetic Parameters

Formal statistical analysis will be performed for KD025 and metabolites KD025m1 and KD025m2 PK parameters as follows:

- Part 1: Cmax, AUC(0-last) and AUC(0-inf)
- Part 2:
  - Primary: Cmax(first dose), Cmax(second dose) and AUC(0-24)
  - Secondary: AUC(0-12), AUC(12-24), AUC(0-last) and AUC(0-inf)

The PK parameters will undergo a natural logarithmic transformation and will be analysed using mixed effect modelling techniques. The model will include terms for treatment fitted as a fixed effect and subject fitted as a random effect.

The following pairwise treatment comparisons (test versus reference) are of interest:

#### Part 1

KD025 200 mg QD + itraconazole (Period 2) vs KD025 200 mg QD alone (Period 1)

Reporting and Analysis Plan KD025-107 (QSC200311) Final v2.0 09 Nov 2018

- KD025 200 mg QD + rabeprazole (Period 3) vs KD025 200 mg QD alone (Period 1)
- KD025 200 mg QD + rifampicin (Period 4) vs KD025 200 mg QD alone (Period 1)

#### Part 2

• KD025 200 mg BID + omeprazole (Period 2) vs KD025 200 mg BID alone (Period 1)

Only subjects who complete both the test and reference treatments within the relevant periods will be included in the statistical analysis. Furthermore for AUC(0-inf) only, a subject must have reliable estimates of AUC(0-inf) for both test and reference treatments within the relative periods to be included in the statistical analysis. If the number of subjects with reliable estimates for both periods is less than 17 (ie less than 50% of planned number of evaluable subjects) then no formal statistical analysis of AUC(0-inf) will be performed ie descriptive summaries only.

The adjusted means including differences from the pairwise comparisons and their associated 90% CIs obtained from the model will be back transformed on the log scale to obtain adjusted geometric mean ratios (GMRs) and 90% confidence intervals (CIs) of the ratios.

In addition, 2 one-sided tests will be performed to obtain the p-value for the test of the null hypothesis of non-equivalence. The one-sided tests will test the following hypotheses against the log transformed lower and upper limits of the equivalence acceptance range.

- Test against the lower limit
  - $H_{01}$ :  $\mu_T \mu_R < \ln(0.7)$
  - $H_{11}$ :  $\mu_T \mu_R \ge \ln(0.7)$
- Test against the upper limit
  - $H_{02}$ :  $\mu_T \mu_R > \ln(1.43)$
  - $H_{12}$ :  $\mu_T \mu_R \le \ln(1.43)$

where H01 and H02 are the null hypothesis (ie test and reference not bioequivalent) for the lower and upper limits respectively and H11 and H12 are the alternative hypothesis (ie test and reference are bioequivalent) for the lower and upper limits respectively.  $\mu_T - \mu_R$ is the difference of the log transformed mean values for test and reference. Each one-sided test will be performed at a 5% significance level ie a p-value of less than 5% indicates there is evidence to reject the null hypothesis of non-equivalence.

Adjusted GMRs and 90% CIs for the adjusted GMRs for the pairwise treatment comparisons listed above, where the ratio is defined as test/reference will be presented. In addition, the largest p-value from the 2 one-sided tests and the intra-subject variability values (denoted as CVw in the results table(s)) will also be presented.

The intra-subject variability values will be calculated for all treatments combined and are obtained from the residual term from the SAS Software output. These values are calculated as follows:

CVw = 100 × [exp(Mean Square Error) - 1]1/2

Reporting and Analysis Plan KD025-107 (QSC200311) Final v2.0 09 Nov 2018 Page 29 of 99 For Part 1, if the 90% CIs for each of KD025 (parent only) Cmax, AUC(0-last) and AUC(0-inf) lie within the acceptance interval of 70.00% to 143.00%, then the absence of an effect on the PK can be concluded for the comparison of interest.

For Part 2, if the 90% CIs for each of KD025 (parent only) Cmax(first dose), Cmax(second dose) and AUC(0-24) lie within the acceptance interval of 70.00% to 143.00%, then the absence of an effect on the PK can be concluded for the comparison of interest.

The model will be fitted using the SAS Software procedure PROC MIXED, the method will specified as Restricted Maximum Likelihood and the denominator degrees of freedom for the fixed effects will be calculated using Kenward and Roger's method [1]. The following is an example of the SAS Software code that will be used:

```
PROC MIXED DATA= METHOD=REML ORDER=INTERNAL;
CLASS SUBJIDN TRTAN ;
MODEL LVAR = TRTAN / OUTP=PRED DDFM=KR;
RANDOM SUBJIDN;
ESTIMATE <relevant pairwise treatment comparisons> / CL ALPHA=0.10;
LSMEANS TRTAN / ALPHA=0.10;
ODS OUTPUT LSMEANS=MEANS ESTIMATES=EST COVPARMS=CVW;
```

RUN;

where

- LVAR is the natural log transformed PK parameter of interest
- SUBJIDN is the numeric subject identifier variable
- TRTAN is the numeric treatment variable for the actual treatment received

Distributional assumptions underlying the statistical analyses will be assessed by visual inspection of residual plots. Normality will be examined by normal probability plots, while homogeneity of variance will be assessed by plotting the residuals against the predicted values for the model. If the distributional assumptions for the parametric approach are not satisfied, the removal of outliers or non-parametric methods might be considered. This will be documented in the CSR together with the reasoning supporting the most appropriate action taken, if applicable.

If there are any deviations from the planned treatment, then the analysis model specified or methods of analysis may be re-evaluated, as appropriate. Details of any deviations from the planned analysis will be documented in the CSR.

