If the 90% CIs for each of KD025 (parent only) Cmax(first dose), Cmax(second dose), and AUC(0-24) lie within the acceptance interval of 70.00% to 143.00%, then the absence of an effect on PK can be concluded for the comparison of interest.

Populations for analysis will be determined for safety and PK data after database lock when the relevant data are available using the criteria defined in the RAP; the RAP will be signed off prior to database lock.

Further details relating to the statistical analysis will be included in the study-specific RAP including the following:

Criteria to be used to define each of the analysis populations

- Additional detail covering the analyses and/or description of primary and secondary analyses and safety data
- Handling of missing data, unused or spurious data
- · Handling of data from withdrawn subjects

All safety and PK data will be listed.

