#### 5.2 Study Sample Size

For the purposes of sample size calculation the following assumptions have been made:

- estimates of intra-subject variability (CVw) of 50% and 40% for Cmax and AUC(0-last), respectively. Data obtained from previous food effect study (QCL117415, data on file)
- two one-sided tests with a probability of type 1 error of 0.05 for PK endpoints Cmax and AUC(0-last), ie 90% CI to be calculated
- acceptance interval of 70.00% to 143.00%
- 80% power assuming the true ratio is between 95.00% and 105.00%

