#### 6.2 Pharmacokinetic Population

The PK population will be defined separately for Part 1 and Part 2 and will include all subjects who have received at least one dose of IMP and who have a minimum of 1 valid post-dose analytical result for PK parameter estimation and who satisfy the following criteria for at least one profile:

- no missing samples at critical time points eg around the Cmax
- no relevant protocol deviations which may impact the study objectives with respect to the PK endpoints and may include any dosing deviations relating to IMP or NIMP
- no relevant AEs such as vomiting which suggest that the dose was not absorbed for a particular subject

The PK populations will be confirmed by Quotient with approval from Kadmon following derivation of all PK parameter estimates.

All subjects will be used for the PK data listings and the PK population will be used for the provision of PK summary statistics, summary tables and figures.

If required, PK analysis datasets will be documented by Quotient with approval from Kadmon at the same time as the PK population. The PK analysis datasets will be a subset of the relevant PK population and will include subjects with sufficient valid PK profiles and who have completed both the test and reference periods for the following pairwise treatment comparisons (test versus reference) to be made ie one PK dataset per comparison):

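### Does the discretion over AUC(0-inf) values leave the Part 1 absence-of-effect rule open to a wrong conclusion?

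*SAP*

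**What the plan says.** The Part 1 rule in SAP 9.2.4, matching Protocol 15.4, needs three parent-drug intervals inside 70.00% to 143.00%: "For Part 1, if the 90% CIs for each of KD025 (parent only) Cmax, AUC(0-last) and AUC(0-inf) lie within the acceptance interval". The Part 2 rule does not use AUC(0-inf).

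For AUC(0-inf) alone, SAP 9.2.4 requires a reliable estimate in both periods of a comparison. SAP 9.2 names two triggers for unreliability, an extrapolated share above 20% or no reliable lambda-z. Such estimates "may be deemed unreliable and excluded from the summary statistics and formal statistical analysis". It adds: "Additional flags may be applied based on emerging data". If fewer than 17 pairs are reliable ("less than 50% of planned number of evaluable subjects) then no formal statistical analysis of AUC(0-inf) will be performed ie descriptive summaries only"), there is no CI.

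On timing, SAP 6.2 states: "The PK populations will be confirmed by Quotient with approval from Kadmon following derivation of all PK parameter estimates". Protocol 15.4 has populations set after database lock, once the data are available, "using the criteria defined in the RAP; the RAP will be signed off prior to database lock". It also lists among the RAP's topics: "Handling of missing data, unused or spurious data".

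SAP 9.1.2 asks for at least 3 lambda-z points not including Cmax, and for a documented peer review of the points chosen.

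**The concern.** A binding entry condition (reliable in both periods) rests on a permissive sentence (may be excluded), and no numerical definition of a reliable lambda-z is given. R-squared below 0.9 and a short regression span are flags without a stated consequence. Two analysts could both follow the SAP and model different sets of AUC(0-inf) values.

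The trial is open label, and the PK populations are confirmed with sponsor approval after the parameters, including each subject's relative bioavailability, have been derived. Period 1 is the reference in all three Part 1 comparisons, so one judgement on a Period 1 profile reaches all of them. If AUC(0-inf) becomes descriptive only, the SAP does not say whether the rule fails, cannot be assessed, or falls back to two parameters. The partial-area fallback in SAP 9.1.2 covers relative bioavailability and metabolite ratios only.

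At stake would be an absence-of-effect statement that depends on a choice made with the results in view.

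**Working it through.** **Inputs.** SAP 5.2: CVw 50% for Cmax and 40% for AUC(0-last), 34 evaluable subjects, limits 0.70 to 1.43, two one-sided 5% tests, true ratio 0.95 to 1.05. Protocol 5.3.2: half-life typically 4 to 8 h, a few longer. Sampling runs to 48 h. No CVw for AUC(0-inf) and no flag rate are given; 40% is assumed for the CVw.

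**1. The plan's own figure.** Paired two one-sided tests with log-scale SE = sqrt(ln(1+CV²)) × sqrt(2/n) and n−1 degrees of freedom. At n = 34 and CVw 50%, power is 80.1% at ratio 0.95 and 80.6% at 1.05, and 34 is the smallest n reaching 80% at 0.95. The stated sample size reproduces. The floor is 17/34 = 50%.

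**2. How often extrapolation would trigger.** For a mono-exponential decline, the share beyond the last quantifiable time is 2^(−t_last/half-life).
- t_last 48 h, half-life 8 h: 2^(−6) = 1.6%.
- 20% at 48 h needs a half-life of 48 × ln2/ln5 = 20.7 h.
- If concentrations are lost after 24 h, an 8 h half-life gives 2^(−3) = 12.5%, and 20% needs 24 × ln2/ln5 = 10.3 h.

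**3. Could dropping prolonged profiles under itraconazole hide an effect?** Assume volume of distribution and bioavailability are unchanged, so AUC rises in proportion to half-life. A typical move from 8 h to 20.7 h then multiplies AUC by 20.7/8 = 2.6. The AUC(0-last) ratio would be about 2.6 × (1 − 0.20)/(1 − 0.016) = 2.1, far above 1.43. AUC(0-last) fails whatever is done with AUC(0-inf).

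**4. Effect of dropping pairs.** For AUC(0-inf) alone at CVw 40% and ratio 0.95, power is 93.6% with 34 pairs, 88.1% with 28 and 62.1% with 17. The full three-parameter rule was simulated with 40,000 trials, SD of the paired difference sqrt(2 ln(1+CV²)), correlation 0.98 between the two AUCs and, in this example, 0.5 between Cmax and AUC, with no extra error in flagged values. At ratio 0.95, 76.3% of comparisons conclude with all pairs, 73.0% with 5 dropped, and 3.6% differ.
- Lost minus gained = 76.3 − 73.0 = 3.3 points; lost plus gained = 3.6 points.
- Gained = (3.6 − 3.3)/2 = 0.15 points; lost = 3.45 points.

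Over Cmax-AUC correlations of 0.5 to 0.9 and added error of SD 0 to 0.3 in flagged values, dropping 3 to 5 pairs at ratio 0.95 creates a conclusion in 0.04% to 1.2% of comparisons. With ratio 0.85 and 8 dropped pairs included, the maximum is about 2.2%. Both ratios lie inside 70% to 143%, so a gained conclusion is a correct one under the trial's own rule.

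**5. False conclusions.** If the true ratio is at or beyond a limit, AUC(0-last) passes at most 5% of the time. The rule also requires AUC(0-last), so it cannot exceed 5% for any choice of AUC(0-inf) values, provided both AUCs share the same true ratio.

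**6. Reaching the floor.** With 34 independent pairs, the chance of 16 or fewer reliable is 0.43% if each is reliable with probability 0.7, and 0.002% at 0.8. Both probabilities are illustrative.

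**7. Reading the rule with no CI.** The rule asks for each of three intervals to lie inside the limits. An interval that does not exist cannot do so, and no conclusion is drawn.

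**The case for a change.** The strongest case for a change is that the protocol handed data handling to the RAP for sign-off before database lock, that replacing a permissive verb with a binding one costs a sentence, and that listing exclusions afterwards is not pre-specification. Varying the assumptions, keeping or dropping 3, 5 or 8 flagged pairs alters the conclusion in 1.2% to 7.3% of comparisons at ratio 0.95.

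The textual part stands: the verb is permissive, a reliable lambda-z is not defined numerically, and the no-CI case is left to inference.

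The rest does not carry a change. Protocol 15.4 itself sets populations after lock when the data are available, so the timing in SAP 6.2 is what the protocol prescribes; its reference to RAP criteria concerns populations of subjects, not single parameter values. The altered conclusions are mainly lost power, at flag rates of 9% to 24% (3/34 to 8/34) that the documents do not support.

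Tighter wording would also not remove the judgement. With fewer than 3 usable points there is no lambda-z, and so no AUC(0-inf) to exclude. Tying reliability to the peer review only moves the undefined term, because that review has no stated criterion. A compulsory 20% cut would always remove the most prolonged profiles, even where the pharmacokineticist judged them sound.

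**Conclusion.** No change follows. This is a gap in detail that a PK analyst fills sensibly. SAP 9.2 names the triggers and SAP 9.1.2 sets the minimum points and the review. SAP 9.2.3 lists all parameters and flags by subject, including extrapolated share, R-squared and the lambda-z limits, so a reader can see any exclusion and check what it did. Read as written, the rule gives no claim when the AUC(0-inf) CI is absent.

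The consequence is small. Exclusions mainly cost power (about 3 points for 5 pairs dropped, in the example above), and AUC(0-last) holds the false-claim rate at 5%. Cmax and AUC(0-last) ratios and CIs are reported in any case. Rabeprazole, with an approximate 80% fall in preliminary data (Protocol 6.1), is far below the 70% limit on any choice. The other two comparisons use a strong inhibitor and a strong inducer of the predominant enzyme, where a pass is not the expected outcome.

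This rests on a CVw of 40% for AUC(0-inf), near mono-exponential decline, half-lives close to the documented 4 to 8 h, and similar true ratios for the two AUCs. Stating the no-CI reading in the SAP would be a courtesy to the reader and would not alter any conclusion.

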#### 9.2.5 Statistical Figures for Analysis of Pharmacokinetic Data

For Part 1, plots of GMRs obtained from the statistical model will be produced for each of the PK parameters: Cmax, AUC(0-last) and AUC(0-inf) for KD025 only, with bars representing the 90% Cls. Plots will include horizontal lines to show lower (ie 70.00%) and upper (ie 143.00%) acceptance limits. Separate plots will be produced for each pairwise comparison of interest.

For Part 2, plots of GMRs obtained from the statistical model will be produced for each of the PK parameters: Cmax(first dose), Cmax(second dose) and AUC(0-24) for KD025 only, with bars representing the 90% CIs. Plots will include horizontal lines to show lower (ie 70.00%) and upper (ie 143.00%) acceptance limits.

## 10 Safety Assessments

Safety data summaries will be presented by actual treatment received in each period and the safety population will be used throughout. Separate summary tables and listings will be produced for each study part.

#### 10.1 Extent of Exposure

The number and percentage of subjects exposed to each study drug on each day (including morning and evening dosing for rabeprazole only in Part 1 and for KD025 only in Part 2) will be summarised by treatment.

#### **10.2 Treatment Compliance**

The total number of scheduled doses will be calculated on the basis of the extent of exposure of each subject for each NIMP. The percentage treatment compliance will be summarised (ie mean, SD, median, minimum, maximum and n) for each NIMP. The evaluation of compliance will be based on the following formula and will be calculated by the Lead Statistical Programmer (or designee) as follows:

Percentage treatment compliance =  $\frac{\text{Total number of administered doses}}{\text{Total number of scheduled doses}} \times 100$ 

If a subject withdraws from the study, their percentage treatment compliance will be calculated for the scheduled doses prior to their withdrawal (ie if a subject receives all scheduled doses up until they withdraw from the study, their percentage treatment compliance will be 100%).

Dosing details (including the date and time of all doses administered) will be listed for all subjects. Any recorded deviations from the planned dosing regimen will be listed as protocol deviations.

